5.3 Lifestyle restrictions

5.3.1 Meals and dietary restrictions

- Refrain from consumption of grapefruit, starfruit, and pawpaw as beverage, fruit or supplements) from 3 days before the start of study medication until after the final dose.
- On Day 1 and Day 8, study participants will be in the fasted state prior to the morning dosing and until approximately 2 hours postdose, and the standard evening meal will be completed approximately 30 minutes prior to dosing.

- On the dosing days (other than Day 1 and Day 8), participants will consume a light meal approximately 30 minutes prior to each morning dose and will consume a standard meal approximately 30 minutes prior to each evening dose. Other meals during the day will be allowed, provided consistent timing and similar meal content are maintained during Treatment Periods. Timing may vary depending on assessments collected in close proximity to meal administration; however, every effort will be made to ensure a consistent meal schedule is adhered to during Treatment Periods. On nondosing days, morning and evening meals will be completed approximately 30 minutes prior to dosing, and other meals (and content) may be consumed at the site's discretion.

Minor departures from the above 30 minute interval are permitted, but the following situations will be handled as protocol deviations:

- No meal is consumed
- Study medication is taken prior to commencing the meal
- Study medication is taken >1 hour following completion of the meal
- Padsevonil will be administered orally with 240mL (8oz) water. Between 1 hour predose and 2 hours postdose, the total intake of beverages should be limited to 100mL. Water will be available ad libitum except for between 1 hour before and 2 hours after dosing.

5.3.2 Caffeine, alcohol, and tobacco

- During each dosing session, participants will abstain from ingesting caffeine- or xanthine-containing products (eg, coffee, tea, cola drinks, and chocolate) for 48 hours before the start of dosing until after collection of the final PK and/or PD sample.
- During each dosing session, participants will abstain from alcohol for 24 hours before the start of dosing until after collection of the final PK and/or PD sample.
- Participants who use tobacco products will be instructed that use of nicotine-containing products (including nicotine patches) will not be permitted while they are in the clinical unit.

5.3.3 Activity

- From Screening through the SFU Visit, participants will abstain from strenuous exercise. Participants may participate in light recreational activities during studies (eg, watching television, reading).

5.4 Screen failures

Screen failures are defined as participants who consent to participate in the clinical study but are not subsequently entered in the study. A minimal set of screen failure information is required to ensure transparent reporting of screen failure participants to meet the Consolidated Standards of Reporting Trials publishing requirements and to respond to queries from regulatory authorities. Minimal information includes demography, screen failure details, eligibility criteria, and any SAE.

5.4.1 Rescreening

Individuals who do not meet the criteria for participation in this study (screen failure) may be rescreened.

Study participants may be rescreened under conditions such as the following:

- Study participant ingests grapefruit (as beverage, fruit, or supplements) within 72 hours before each administration of study medication.
- If a study participant does not meet the exclusion criteria at the Screening Visit (Days -21 to -2) or at the Baseline Visits (Day -1 of each Treatment Period) due to an out-of-range laboratory result or a minor illness, he/she can be rescreened once, at the discretion of the Investigator.
- Study participant may be included if the repeat values for the laboratory screening criteria are within normal ranges and/or if repeat values show normalization of the out-of-range safety laboratory values, and/or after the study participant makes a complete recovery from the mild or moderate illness, and if all other screening criteria are met.
- Rescreened participants should be assigned the same participant number as for the initial screening.
- Tests that result in ALT, AST, or ALP up to 25% above the exclusion limit may be repeated once for confirmation. This includes rescreening.

6 STUDY TREATMENTS

Study treatment is defined as any investigational treatment(s), marketed product(s), placebo, or medical device(s) intended to be administered to a study participant according to the study protocol. Further guidance and information regarding study treatments are provided in the UP0050 Investigational Medicinal Product (IMP) Handling Manual.

6.1 Treatments administered

A summary of the treatments administered is provided in [Table 6-1](#). Further guidance or information is provided in the IMP Handling Manual.

Table 6-1: Treatments administered

Study Treatment Name:	PSL	Moxifloxacin	Placebo
Dosage formulation:	Tablet	Tablet	Tablet
Dosage levels:	100mg, 200mg, 300mg, and 400mg bid	400mg	To match PSL 100mg, 200mg, 300mg, and 400mg bid
Route of administration:	Oral	Oral	Oral
Dosing instructions:	Dosing instructions are provided in the UP0050 IMP Handling Manual (IP Instruction for Handling).		
Packaging and labeling:	Padsevonil tablets are manufactured, packaged, and labeled according to GMP guidelines and applicable laws or regulations.	Moxifloxacin tablets are manufactured, packaged, and labeled according to GMP guidelines and applicable laws or regulations.	Placebo to match PSL tablets are manufactured, packaged, and labeled according to GMP guidelines and applicable laws or regulations.
Manufacturer:	UCB	Accord Healthcare Ltd.	UCB

bid=twice daily dosing; GMP=Good Manufacturing Practice; IMP=investigational medicinal product; IP=investigational product; PSL=padsevonil

6.2 Preparation, handling, storage, and accountability requirements

The Investigator or designee must confirm appropriate temperature conditions have been maintained during transit for all study medications received and any discrepancies are reported and resolved before use of the study medication.

Only participants enrolled in the study may receive study medication, and only authorized site staff may supply or administer study medication. All study medications must be stored in a secure, environmentally controlled, and monitored (manual or automated) area in accordance with the labeled storage conditions with access limited to the Investigator and authorized site staff.

The Investigator, institution, or the head of the medical institution (where applicable) is responsible for study medication accountability, reconciliation, and record maintenance (ie, receipt, reconciliation, and final disposition records).

In case an out-of-range temperature is noted, it must be immediately reported as per instructions contained in the UP0050 IMP Handling Manual.

Further guidance and information for the final disposition of unused study medication are provided in the UP0050 IMP Handling Manual.

6.2.1 Drug accountability

A Drug Accountability form will be used to record study medication dispensing and return information on a by-participant basis, and will serve as source documentation during the course of the study. Details of any study medication lost, damaged (due to breakage or wastage), not used, partially used, disposed of at the study site, or returned to the Sponsor or designee must also be recorded on the appropriate forms. All supplies and pharmacy documentation must be made available throughout the study for UCB (or designee) to review.

The Investigator (or designee) is responsible for retaining all used, unused, and partially used containers of study medication until returned or destroyed.

The Investigator may assign some of the Investigator's duties for drug accountability at the study site to an appropriate pharmacist/designee.

The Investigator must ensure that the study medication is used only in accordance with the protocol.

Periodically, and/or after completion of the clinical phase of the study, all used (including empty containers)/partially used, unused, damaged, and/or expired study medication must be reconciled and either destroyed at the site according to local laws, regulations, and UCB Standard Operating Procedures (SOPs) or returned to UCB (or designee). Study medications intended for the study cannot be used for any other purpose than that described in this protocol.

6.3 Measures to minimize bias: randomization and blinding

A contract research organization (CRO; ie, ICON) randomization biostatistician will create the program to generate the randomization code and code break envelopes. The randomization biostatistician will be independent of the study. A dummy randomization schedule will be prepared by the randomization biostatistician (ICON) and reviewed by the Clinical Study Biostatistician in order to ensure that the code meets the study requirements.

After finalization of the dummy code, the randomization program will be run with a different seed number to create the final randomization list; the final list will be generated in a secure environment and will be reviewed by a quality control randomization biostatistician, also independent of the study. This randomization list will be retained by the unblinded randomization biostatistician and study pharmacist until the end of the study (ie, until after database lock). The treatment assignment will be random.

Copies of the randomization lists will be sent before the start of the study in a secure fashion directly from the contracted CRO to:

- Sponsor Patient Safety (PS) staff for SAE reporting (sealed envelope)
- Bioanalytical staff (to identify samples to be measured)
- Unblinded member of pharmacy involved in study medication preparation and dispensing
- Independent Biostatistician/Early Statistical Programmer

In addition, staff involved in the analysis of unblinded PK data, such as a representative from the UCB Clinical Pharmacology/ Modeling and Simulation team and an unblinded monitor, will have access to the unblinded data during the study.

At Screening, each study participant will be assigned a unique 5-digit study participant number from a range of numbers supplied by UCB Clinical Data Operations, Technology, and Standards.

Once the Investigator determines that the study participant is eligible for the study, and before study medication administration, a central person in charge of issuing the randomization numbers will manually allocate a randomization number to the study participant (one for each study part) and communicate the randomization assignment to the unblinded site pharmacist. Each specific randomization number will be linked to the treatment allocation on the randomization schedule, which will be dispensed by the unblinded site pharmacist. The randomization numbers will also be recorded in the eCRF.

6.3.1 Procedures for maintaining and breaking the treatment blind

6.3.1.1 Maintenance of study treatment blind

All participant treatment details (treatments, Treatment Period, and treatment sequences) will be allocated and maintained through the use of randomization lists and code break envelopes (or equivalent).

6.3.1.1.1 PSL and matching placebo

A site pharmacist who is not a member of the study team (has no responsibilities for study participant assessments) will prepare PSL or PSL placebo treatment from bulk supplies in accordance with the randomization schedule supplied by the ICON unblinded randomization statistician.

6.3.1.2 Breaking the treatment blind in an emergency situation

A code break envelope (or equivalent) containing the randomization code will be printed for each participant in a double-blind study and must not be broken, except for emergency situations. The Clinical Project Manager (CPM) must be informed immediately when a code is broken, but should remain blinded to specific treatment information. Any unblinding of the study medication

performed by the Investigator must be recorded in the source documents and on the Study Termination eCRF page.

6.4 Treatment compliance

Study participant compliance will be ensured by the administration of study medication by designated site personnel. Drug accountability must be recorded on the Drug Accountability form.

6.5 Concomitant medications/treatments

6.5.1 Permitted concomitant treatments (medications and therapies)

The following concomitant medications are permitted during the study:

- Paracetamol/acetaminophen for the treatment of mild symptoms (eg, headache or other pain), given at most every 6 hours to 8 hours, not exceeding 2g per day, and with a total of no more than 5g over 7 days.
- Ibuprofen, not exceeding 1.2g per day.
- Inhaled corticosteroids for seasonal rhinitis and topical corticosteroids for controlled dermatological conditions.
- Oral contraceptives not exceeding 30µg ethinyl estradiol or postmenopausal hormone replacement therapy or implants, patches, or intrauterine devices/intrauterine systems delivering progesterone (for female study participants).

6.5.2 Prohibited concomitant treatments (medications and therapies)

With the exception of permitted concomitant treatments listed in Section 6.5.1, the following concomitant medications are prohibited during the study:

- All prescription or nonprescription medicines, are prohibited within 2 weeks or 5 half-lives (whichever is longer) before administration of study medication and during the clinical part of the study, unless required to treat an AE. This includes all OTC remedies, vitamins, and herbal and dietary supplements (including St John's Wort).
 - Hepatic enzyme-inducing drugs (eg, glucocorticoids, phenobarbital, isoniazid, phenytoin, rifampicin, etc.) should not be used within 2 months prior to dosing. In case of uncertainty, the UCB Study Physician should be consulted.
- Drugs of unknown half-lives are prohibited within 2 weeks before administration of study medication and during the clinical part of the study, unless required to treat an AE.

If a study participant needs or takes any prohibited medication, the Investigator will (where possible) discuss with the Sponsor Study Physician and a decision will be made whether the study participant can continue in the study or must be withdrawn.

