7.2 Participant discontinuation/withdrawal from the study

Study participants are free to withdraw from the study at any time, without prejudice to their continued care.

A study participant may withdraw from the study at any time at his/her own request, or may be withdrawn at any time at the discretion of the Investigator for safety, behavioral, compliance, or administrative reasons.

If the study participant withdraws consent for disclosure of future information, the Sponsor may retain and continue to use any data collected before such a withdrawal of consent.

If a study participant withdraws from the study, he/she may request destruction of any samples taken and not tested, and the Investigator must document this in the site study records.

See the Schedule of activities ([Table 1-1](#)) for data to be collected at the time of study discontinuation and follow-up and for any further evaluations to be completed.

Study participants should be withdrawn from the study if any of the following events occur:

1. Study participant develops a clinically relevant medical condition (physical or psychiatric) that, in the opinion of the Investigator, jeopardizes or compromises the study participant's ability to participate in the study or makes it unsafe to continue.
2. Study participant is noncompliant with the study procedures or medications in the opinion of the Investigator.
3. Study participant takes prohibited concomitant medications as defined in this protocol.
4. Study participant withdraws his/her consent.
5. The Sponsor or a regulatory agency requests withdrawal of the study participant.
6. Study participant has changes in the ECG that are regarded as clinically significant and/or that worsens over time. An ECG shows an absolute value for QTcB or QTcF $\geq 500\text{ms}$ or $\geq 60\text{ms}$ above Baseline.
7. Study participant develops second- or third-degree atrioventricular block or another clinically relevant change in ECG as determined by the Investigator.
8. Participant has active suicidal ideation without a specific plan as indicated by a positive response ("Yes") to Question 4 of the "Since Last Visit" version of the C-SSRS. The study participant should be referred immediately to a mental healthcare professional and may be withdrawn from the study based upon the Investigator's judgment of the benefit/risk ratio of continuing the study participant in the study on PSL.

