 - Participant has active suicidal ideation with a specific plan as indicated by a positive response ("Yes") to Question 5 of the "Since Last Visit" version of the C-SSRS. The study participant should be referred immediately to a mental healthcare professional and must be withdrawn from the study.
9. Study participant is suspected of having a serious multiorgan hypersensitivity reaction. Serious suspected multiorgan hypersensitivity cases may be identified and reported to the Sponsor by the Investigator using the following algorithm:
 - An AE or laboratory value (as defined below) suggestive of internal organ involvement including but not limited to hepatitis, nephritis, pneumonitis, carditis, colitis, encephalitis, pancreatitis, myositis, arthritis, or hematologic system involvement combined with at least 1 of the following: fever, rash, lymphadenopathy, or eosinophilia.
 - Treatment-emergent abnormal laboratory value criteria suggestive of internal organ involvement or eosinophilia:
 - Eosinophils percentage $\geq 10\%$.
 - Eosinophils absolute $\geq 0.5\text{G/L}$.

- Neutrophils absolute <1.5G/L.
- Platelets absolute \leq 100G/L.

Withdrawn study participants should follow the Taper schedule if possible, unless faster discontinuation is considered necessary in the medical judgement of the Investigator. Investigators should attempt to obtain information on study participants in the case of withdrawal.

Investigators should contact the UCB Study Physician, whenever possible, to discuss the withdrawal of a participant in advance.

Participants withdrawn may be replaced at the discretion of the Investigator and Sponsor.

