9.1 Definition of analysis sets

The following are the defined analysis sets:

- Enrolled Set (ES): All study participants who have signed the ICF.
- Randomized Set (RS): All enrolled study participants who are randomized will be included in the RS.
- Safety Set (SS): All enrolled study participants who receive at least 1 dose of study medication.
- Pharmacokinetic Per-Protocol Set (PK-PPS): All enrolled study participants who receive at least 1 dose of study medication and who have no important protocol deviations affecting the PK and for whom at least 1 measurable concentration is available.

For definitions of the Pharmacodynamic Per-Protocol Set (PD-PPS) and other relevant PD analysis sets, refer to the SAP.

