9.7 Handling of protocol deviations

Important protocol deviations are deviations from the protocol which potentially could have a meaningful impact on study conduct or on the primary PK outcome (or primary PD outcome) for an individual study participant. Study participants will be excluded from the PK-PPS (or PD-PPS) only when there is documented evidence that they received no treatment. The criteria for identifying important protocol deviations and the classification of important protocol deviations will be defined within the relevant protocol deviation specification document, which is part of the study Data Cleaning Plan. To the extent feasible, rules for identifying protocol

deviations will be defined without review of the data and without consideration of the frequency of occurrence of such deviations. Whenever possible, criteria for identifying important protocol deviations will be implemented algorithmically to ensure consistency in the classification of important protocol deviations across all study participants.

Important protocol deviations will be reviewed as part of an ongoing blinded data cleaning process prior to database lock to confirm exclusion from analysis sets.

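### Section 9.7 allows exclusion from the per-protocol sets only for untreated participants, contradicting Section 9.1 and its own deviation review; 6.5.2 and 7.2 item 3 also differ, mildly, on prohibited medication

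*Protocol*

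**What the plan says.** **Per-protocol sets.** Section 9.1 limits the PK-PPS to participants with at least one dose of study medication "who have no important protocol deviations affecting the PK and for whom at least 1 measurable concentration is available". It leaves the PD-PPS definition to the SAP. Section 9.7 defines important deviations by their possible impact on study conduct or on the primary PK or PD outcome. It then states: "Study participants will be excluded from the PK-PPS (or PD-PPS) only when there is documented evidence that they received no treatment". It ends by having important deviations reviewed "as part of an ongoing blinded data cleaning process prior to database lock to confirm exclusion from analysis sets".

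**Prohibited medication.** Section 6.5.2 has the Investigator discuss the case with the Study Physician where possible, after which "a decision will be made whether the study participant can continue in the study or must be withdrawn". Section 7.2 opens its list with "Study participants should be withdrawn from the study if any of the following events occur", and item 3 of that list reads "Study participant takes prohibited concomitant medications as defined in this protocol". Section 7.2 later adds: "Investigators should contact the UCB Study Physician, whenever possible, to discuss the withdrawal of a participant in advance".

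**The concern.** A per-protocol set exists to leave out participants whose conduct departs enough from the protocol to distort the outcome. The word 'only' in Section 9.7 removes that function. A participant who received study medication cannot be excluded, whatever the deviation. Section 9.1 says the opposite for the PK-PPS, and the review at the end of 9.7 presupposes the opposite for both sets. Two analysts following the same protocol could build two different PK sets, and each could cite a section in support.

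At stake is who enters the PK summaries at steady state, which are secondary endpoints, and whether the SAP can define a deviation-based PD-PPS without contradicting its protocol.

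The second point concerns conduct. In a three-period crossover, withdrawal after a prohibited drug ends collection of the remaining periods. The site needs to know whether withdrawal is the default or one of two open options, and the SAP cannot settle that afterwards.

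**Working it through.** The point is textual, and no figure in the protocol bears on it. The check is to apply each section to the same participant.

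**PK-PPS, Section 9.1 against the 9.7 sentence**

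1. *Never dosed.* Under 9.1: out, by the dose requirement. Under 9.7: out. They agree, so 9.7 adds nothing here.
2. *Dosed, measurable concentration, no important deviation.* In under both.
3. *Dosed, measurable concentration, important deviation affecting PK.* Under 9.1: out. Under 9.7: in, because treatment was received. They conflict.
4. *Dosed, no measurable concentration*, for example someone who leaves after a placebo period only. Under 9.1: out. Under 9.7, read literally: in. They conflict again.

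The 9.7 sentence thus removes nobody whom the 9.1 dose requirement had not already removed. Its only literal effect is to cancel the other conditions of 9.1.

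**Section 9.7 against itself**

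The section defines important deviations by their impact on the outcome and has them reviewed under blind to confirm exclusions. If the sole ground for exclusion is that no treatment was received, that review has nothing to confirm except non-receipt.

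**Possible harmonising readings**

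- *Non-receipt is the one deviation that leads to exclusion.* The deviation clause of 9.1 would then only repeat its own dose requirement.
- *'No treatment' is meant by period.* The sentence would then have some content in a crossover. But it speaks of participants and mentions no period, and case 3 would still be in conflict.

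Neither reading reconciles the sections.

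**PD-PPS**

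Section 9.1 gives no definition, so there is no second protocol rule to contradict directly. Section 9.7 nevertheless names the PD-PPS in its restriction. An SAP that excludes treated participants for PD-relevant deviations would depart from 9.7. An SAP that obeys 9.7 would exclude no treated participant for a deviation.

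**Section 6.5.2 against Section 7.2 item 3**

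- The event is the same: a prohibited medication is taken.
- 6.5.2: a decision, with continuation as one possible outcome.
- 7.2 item 3: a listed reason for withdrawal, with no judgement clause and no cross-reference.
- Elsewhere in 7.2 the degree of discretion is spelled out. The item on C-SSRS Question 4 lets the Investigator's judgement decide, and Question 5 carries a 'must'. Item 3 has neither, so its status is unclear.
- Drugs needed to treat an adverse event fall outside this. The prohibition on medicines applies "during the clinical part of the study, unless required to treat an AE", so such use triggers neither rule.

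**The case against.** **Intent is clear from context.** Read as a whole, Section 9.7 evidently wants ordinary deviation-based exclusions, and a sensible SAP author would write them. This stands as a guess at intent. It does not change the sentence, which says 'only' and names both sets.

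**The PD-PPS belongs to the SAP.** Largely right. The contradiction inside the protocol concerns the PK-PPS, and the PK endpoints are secondary or other. For the PD-PPS, the most that can be said is that 9.7 would conflict with a deviation-based definition if the SAP contains one.

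**The withdrawal rules can be read together.** Section 7.2 says 'should', and it asks for contact with the Study Physician before a withdrawal. The 6.5.2 decision fits that as the specific rule under a general list. Dropouts may also be replaced. Most of this stands, and what remains is a missing cross-reference.

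**A stronger reading that might be inferred.** A reader might conclude that a participant given a QTc-active drug for an adverse event must stay in the primary analysis and would bias the QTcF contrast. The documents do not support this:

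- Such treatment is exempt under 6.5.2. It need not be a deviation, so it triggers neither the withdrawal rules nor the deviation clause of 9.1.
- Section 9.4.1 does not say which set the primary analysis uses.
- Section 9.7 governs participants, so the SAP could still omit single ECG time points.
- The protocol gives neither the frequency of such use nor the size of any QTc shift. Any bias or power figure would rest on assumption alone.

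**Conclusion.** The point holds as an internal contradiction of minor severity. As written, the exclusion sentence in Section 9.7 cannot be followed together with the PK-PPS definition in 9.1 or with the closing sentence of 9.7. The mismatch between 6.5.2 and 7.2 item 3 is real but milder.

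No numerical effect is claimed. The planned 49 evaluable participants and the stated 96% power are untouched, and no bias in the primary QTc result is shown. The conclusion assumes that 'only' carries its ordinary meaning and that 'no treatment' refers to the participant's whole participation. Under a by-period reading the conflict narrows but remains. The SAP is not at hand. It may define workable sets, but doing so would leave the protocol sentence wrong.

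**What to change.** 1. In Section 9.7, replace the 'only' sentence with wording such as: *Participants with an important protocol deviation that affects the PK are excluded from the PK-PPS, and those with one that affects the primary PD outcome from the PD-PPS, as confirmed at the blinded review before database lock.* This matches 9.1, gives the planned review its purpose, and leaves the detailed criteria to the deviation specification document and the SAP.
2. In Section 7.2, reword item 3 along these lines: *Participant takes a prohibited concomitant medication and the decision under Section 6.5.2 is to withdraw.*

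The cost is two sentences in the next amendment. Sample size, data collection, the ECG analysis and the treatment of adverse events stay as they are. A rule for omitting ECGs recorded near QTc-active co-medication is not needed to resolve either contradiction. It would be a matter for the SAP.
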